5.2.3 Step-Down Therapy

The IDSA clinical practice guidelines for treatment of Candidiasis recommend that the total duration of therapy for candidemia is 14 days after documented clearance of *Candida* spp. from the bloodstream (i.e., first consecutive negative blood culture) and resolution of symptoms attributable to candidemia. Hence, the duration of antifungal treatment required to treat patients

with candidemia in this study will be driven by the time to clearance of candidemia. In 3 randomized controlled trials in candidemia and invasive Candidiasis, the median time to bloodstream infection clearance after receiving appropriate antifungal therapy was 2 to 3 days. Therefore, patients enrolled in this study may need a few additional days of fluconazole therapy (unless susceptibility results warrant alternative antifungal therapy) for a total duration of antifungal treatment of approximately 16 to 17 days. Likewise, any patients who have deep-seated sites of infections diagnosed after enrollment, while they can continue to receive APX001 study drug treatment per protocol, will require additional days of fluconazole therapy.

If appropriate, additional antifungal drug therapy with fluconazole (unless susceptibility results warrant alternative antifungal therapy) can be administered beyond 14 days of APX001. The recommended dose of fluconazole is 800 mg QD on the first day followed by 400 mg QD, for a maximum of 7 days.

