7.5.2 Cultures From Other Sites of Infection

Any *Candida* spp. cultured from a normally sterile site, from intravascular catheter tip(s), or from a sample indicative of deep-seated invasive Candidiasis discovered after dosing with APX001, should be sent to the mycology reference laboratory for confirmation of identification and susceptibility testing.

7.5.3 *Candida* Spp. Testing by T2 Magnetic Resonance Assay

Each time a blood culture is collected for the protocol, an additional blood sample will be collected for *Candida* spp. testing by T2MR assay at Baseline, during Study Drug Treatment, and through EOST or Early Termination. A central laboratory will perform the T2MR assay.

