6.4. Definitions for Efficacy Assessments

6.4.1. At End of Study Drug Treatment (EOST)

Treatment Success is defined as meeting all of the following criteria:

- Two consecutive blood cultures negative for *Candida* spp.;
- Alive at EOST; and
- No concomitant use of any other systemic antifungal therapies through EOST.

Treatment Failure is defined as any case that does not meet the criteria for Treatment Success.

Mycological Outcome:

• Eradication is defined as a negative blood culture(s) for *Candida* spp. in the absence of concomitant antifungal therapy through EOST.

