6.4.3. At Follow-up (2 Weeks and 4 Weeks After End of Antifungal Treatment)

- Recurrence (mycological) is defined as a mycologically confirmed infection based on blood culture with the same Baseline *Candida* spp. during the 4 weeks after EOT.
- Relapse (DRC Assessment) is defined as re-occurrence of *Candida* in blood culture during the Follow-up Period, or diagnostic parameters indicative of recurrence or late spread of the *Candida* infection.

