7.4. Efficacy Analysis

7.4.1. Primary Efficacy Analysis

The primary efficacy endpoint is Treatment Success at EOST as determined by the DRC.

The number and percentage of patients with Treatment Success or Treatment Failure at EOST determined by the DRC will be summarized descriptively in total for the MITT Population. The 95% two-sided exact binomial confidence interval will also be presented.

Additional analyses of the primary efficacy endpoint will be performed for the PP Population in the same manner.

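### As written, a patient whose blood clears is a Treatment Success at EOST and EOT even if a new deep-site Candida infection is documented on treatment, while late spread after EOT counts as Relapse

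*SAP*

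**What the plan says.** The primary analysis (SAP 7.4.1) reads: "The primary efficacy endpoint is Treatment Success at EOST as determined by the DRC". SAP 6.4.1, matching Protocol 7.4.1, gives three criteria for Success at EOST:

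- blood: "Two consecutive blood cultures negative for" Candida species;
- survival to EOST;
- antifungals: "No concomitant use of any other systemic antifungal therapies through EOST".

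Failure is the complement: "Treatment Failure is defined as any case that does not meet the criteria for Treatment Success". SAP 6.4.2 repeats this structure at EOT but exempts protocol-allowed step-down, with fluconazole as the example. Eradication, the mycological outcome at both visits, also rests on blood cultures.

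The protocol foresees deep infection that comes to light later. Section 5.2.3, repeated in 5.6.3, covers "any patients who have deep-seated sites of infections diagnosed after enrollment, while they can continue to receive APX001 study drug treatment per protocol", and says that they will then need further fluconazole. Section 7.5.2 sends to the reference laboratory any Candida cultured "from a sample indicative of deep-seated invasive Candidiasis discovered after dosing with APX001".

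At follow-up the rule is broader. Relapse, assessed by the DRC, includes "diagnostic parameters indicative of recurrence or late spread of the" Candida infection (SAP 6.4.3).

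**The concern.** The plan accepts evidence from outside the blood as a bad outcome after antifungal treatment ends, but gives it no role while APX001 is being given, which is the period the primary endpoint measures. No reason for the difference is stated. The endpoint is named Treatment Success, and the primary objective is efficacy in treating candidemia, so many readers will take the rate as overall success. If some patients counted as successes had a newly documented deep-site infection on treatment, the planned tables would not show how far the rate depends on them.

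**Working it through.** **Step 1. Follow one patient through the definitions.** Take a patient whose blood cultures turn negative, who survives, who has a deep or sterile-site Candida infection first documented after the first dose, and who receives APX001 and then fluconazole within the allowed step-down.

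| Stage | Rule | Result as written |
|---|---|---|
| EOST | SAP 6.4.1: blood, survival, no other antifungal | All three met: Success |
| EOT | SAP 6.4.2: same, step-down exempt | All met: Success |
| Reasons for failure | SAP 7.4.2.5: cultures not negative, additional antifungals, death, withdrawal | No row applies |
| Carry-forward | SAP 7.1.2: an earlier clinical failure is carried forward | No failure to carry |
| 2 and 4 weeks after EOT | SAP 7.4.2.1: Treatment Success Sustained, Clinical Relapse, or Other (Non-Relapse) | Not settled |

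The last row is open because a site already known during treatment is not obviously late spread. Such a patient could end as Treatment Success Sustained.

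**Step 2. Look for another analysis that would show the case.** Other-site cultures, histopathology and imaging are done when clinically indicated (SAP 2.2), but no efficacy summary uses them. SAP 7.4.4 lists remaining efficacy data by patient.

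**Step 3. Size.** The sample size is about 20, with no formal calculation (SAP 3), so the plan has no figure to reproduce. The observed success counts and the number of deep-site cases below are assumptions, because the documents give neither. If k of x successes are reclassified, the rate is (x − k)/20, so each case costs 1/20 = 5 points. The interval is the exact binomial one named in SAP 7.4.1. For y successes in n, the lower limit is the 2.5th percentile of Beta(y, n − y + 1) and the upper limit is the 97.5th percentile of Beta(y + 1, n − y).

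| Assumed successes | k = 0 | k = 1 | k = 2 | k = 3 |
|---|---|---|---|---|
| 18/20 | 90% (68.3–98.8) | 85% (62.1–96.8) | 80% (56.3–94.3) | 75% (50.9–91.3) |
| 16/20 | 80% (56.3–94.3) | 75% (50.9–91.3) | 70% (45.7–88.1) | 65% (40.8–84.6) |
| 14/20 | 70% (45.7–88.1) | 65% (40.8–84.6) | 60% (36.1–80.9) | 55% (31.5–76.9) |

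**Step 4. Chance of meeting the case at all.** With a per-patient probability p, the chance of at least one case among 20 is 1 − (1 − p)^20. For assumed p of 5%, 10% and 15%:

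- 1 − 0.95^20 = 64%, with 1 case expected;
- 1 − 0.90^20 = 88%, with 2 expected;
- 1 − 0.85^20 = 96%, with 3 expected.

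**The case against.** The indication is candidemia. Blood clearance with survival and no other antifungal is an objective and legitimate endpoint, and the rate estimates that endpoint correctly. The study is single-arm and descriptive, with no hypothesis, success threshold or interim analysis, so no formal decision turns on a few points. The DRC determines the outcome under a charter that is not among the documents and may already cover deep sites. Another systemic antifungal given before EOST already makes the case a Failure. The information is not lost either: it is listed by patient and, under the broad adverse event definition, would ordinarily be recorded as a treatment-emergent event, although the documents do not say so specifically.

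All of this stands, and it limits the point. It rules out three stronger readings that a reader might infer:

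- **That every deep site found on treatment is spread, and so a drug failure.** The protocol speaks only of diagnosis after enrollment. Known deep-seated disease is an exclusion (Protocol 4.2), so a site found later may be undetected entry disease.
- **That on-treatment failures are moved into the relapse count.** A site already known during treatment may not qualify as late spread, so this route is speculative.
- **That the primary definition must be rewritten.** That is a debatable trade-off and would need a protocol amendment. It would also tie the primary outcome in an open-label study to imaging and cultures done only when clinically indicated, and to fundoscopy that after Screening is required only in patients with positive Screening findings.

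The objection does not remove the gap in the written plan. The SAP's own list of DRC failure reasons has no deep-site item, and a reader should not need an unseen charter to know how a case foreseen in the protocol is counted.

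**Conclusion.** The point holds on the written definitions for a limited group: patients whose blood clears, who survive, who receive only APX001 and allowed step-down, and in whom a sterile or deep-site Candida infection is newly documented after the first dose. They are Successes at EOST and EOT, and their follow-up category is undetermined. Each is worth 5 percentage points at n=20. A range of 0 to 3 cases, or 0 to 15 points, is an assumption; the true frequency may be zero.

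A reader might go further and say that the primary rate is biased upward or hides failures. The documents do not support that: the rate is unbiased for the endpoint as defined, the number of cases is unknown, and the DRC may classify them under its charter. What is established is an unexplained difference between the on-treatment and follow-up definitions, with no planned analysis to show its effect.

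**What to change.** Keep the primary definition and make three additions to the SAP:

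1. **7.4.1, sensitivity analysis (MITT and PP Populations).** Count as Failure any patient with a DRC-confirmed Candida infection newly documented at a normally sterile or deep site after the first dose through EOST. Apply the same rule through EOT for the analysis in 7.4.2.1. For each case the DRC records whether it judges the infection to be new spread or disease present at entry, so that the two are kept apart in the report.
2. **7.4.2.5, descriptive row.** Add deep-site Candida infection on treatment.
3. **6.4.3 and 7.4.2.1, follow-up.** State how these patients are classified at 2 and 4 weeks after EOT.

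This concerns outcome classification only and leaves treatment unchanged. The cost is SAP wording and a field on the DRC form, with no new procedures and no change to the primary endpoint. The SAP is to be finalized before database lock, so the rule can still be pre-specified. The sensitivity rate may be slightly lower. Because it depends on imaging, other cultures, histopathology and fundoscopy done largely when clinically indicated in an open-label study, it should be read as supportive.

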6.4.2. At End of Antifungal Treatment (EOT)

After completion of 14 days study drug therapy, if further antifungal treatment is indicated to complete treatment of candidemia in accordance with standard practice guidelines, fluconazole (unless susceptibility results warrant alternative antifungal therapy) may be administered for up to a further 7 days. If applicable, an assessment of efficacy will also be made at the end of this antifungal treatment at EOT.

Treatment Success is defined as meeting all of the following criteria:

- Two consecutive blood cultures negative for *Candida* spp.;
- Alive at EOT; and
- No additional systemic antifungal therapies (except for protocol-allowed step-down treatment [e.g., fluconazole]) through EOT.

Treatment Failure is defined as any case that does not meet the criteria for Treatment Success.

Mycological Outcome:

• Eradication is defined as a negative blood culture(s) for Candida spp. in the absence of additional antifungal therapy (except for protocol-allowed step-down treatment [e.g., fluconazole]) through EOT.

6.4.3. At Follow-up (2 Weeks and 4 Weeks After End of Antifungal Treatment)

- Recurrence (mycological) is defined as a mycologically confirmed infection based on blood culture with the same Baseline *Candida* spp. during the 4 weeks after EOT.
- Relapse (DRC Assessment) is defined as re-occurrence of *Candida* in blood culture during the Follow-up Period, or diagnostic parameters indicative of recurrence or late spread of the *Candida* infection.

6.5. Microbiological Assessments

6.5.1. Blood Cultures

A blood culture positive for *Candida* spp. drawn within 96 hours of APX001 dosing is required for eligibility as part of SOC. During screening, 2 consecutive sets (1 aerobic and 1 anaerobic blood culture bottle per set) of blood cultures from 2 separate sites (1 from a central venous catheter [CVC] and 1 peripheral venipuncture, or 2 peripheral venipunctures, if a CVC is not applicable) are required before the initiation of APX001 dosing. The screening cultures may be drawn on the day of dosing. Blood cultures (minimum of 1 set) for *Candida* spp. will also be performed at Baseline (pre-dose), during Study Drug Treatment, at EOST, EOT, and 2 and 4 weeks after EOT, or Early Termination. During the Study Drug Treatment Period, daily blood cultures are required on Study Days 1 through 4; thereafter, blood cultures may be stopped after negative results on 2 consecutive days are obtained. *Candida* spp. isolates from the blood cultures performed at the local laboratory must be submitted to the mycology reference laboratory for confirmation of identification and susceptibility testing.

If a Sponsor-approved rapid diagnostic test for candidemia is used to identify potentially eligible patients, subsequent confirmatory blood cultures are required prior to dosing. Likewise, *Candida* spp. isolates from these blood cultures are to be submitted to the mycology reference laboratory. Results from any further rapid diagnostic tests performed as per local SOC must be captured in the eCRF.

6.5.2. Cultures from Other Sites of Infection

Any *Candida* spp. cultured from a normally sterile site, from intravascular catheter tip(s), or from a sample indicative of deep-seated invasive Candidiasis discovered after dosing with APX001, should be sent to the mycology reference laboratory for confirmation of identification and susceptibility testing.

6.5.3. Candida Spp. Testing by T2 Magnetic Resonance Assay

Each time a blood culture is collected for the protocol, an additional blood sample will be collected for *Candida* spp. testing by T2MR assay at Baseline, during Study Drug Treatment, and through EOST or Early Termination. A central laboratory will perform the T2MR assay.

6.5.4. Intravascular Catheter Management and Log

If possible, all indwelling intravascular catheters should be removed and the catheter tips cultured prior to starting APX001 dosing. The entrance site should also be cultured if it appears infected. Intravascular catheter management should be managed at the site level as per local SOC.

6.6. **Safety Endpoints**

Safety assessments will include adverse events, vital signs, clinical laboratory evaluations, physical examination, and ECGs.

6.6.1. **Adverse Events**

An adverse event is defined as any untoward medical occurrence in a clinical investigation patient administered a pharmaceutical product, which does not necessarily have a causal relationship with this treatment. An adverse event can therefore be any unfavorable and/or unintended sign (including an abnormal laboratory finding), symptom, or disease temporally associated with the use of a study drug, whether or not related to the study drug. All adverse events, including observed or volunteered problems, complaints, or symptoms, are to be recorded on the appropriate eCRF.

6.6.2. **Clinical Laboratory Evaluations**

Screening laboratory assessments to determine eligibility will be performed at the local laboratory and may have been collected as SOC within the previous 24 hours. Laboratory assessments collected after Screening will be sent to the central laboratory for analysis.

Clinical laboratory assessments (serum chemistry, hematology, coagulation, and urinalysis) will occur at Screening, Baseline (pre-dose), twice weekly during Study Drug Treatment, at EOST, EOT, and 2 and 4 weeks after EOT, or Early Termination. If clinically indicated and at the discretion of the Investigator, or if a suspected adverse event is identified, clinical laboratory assessments may be conducted at any time during the study and compared to Baseline. The following is a complete list of clinical laboratory analytes.

Standard Safety Chemistry Panel

Alanine aminotransferase	Albumin			
Alkaline phosphatase	Amylase			
Aspartate aminotransferase	Bicarbonate			
Bilirubin (total, direct, and indirect)	Blood urea nitrogen			
Calcium	Chloride			
Creatine kinase	Creatinine			
Estimated glomerular filtration rate	Gamma-glutamyl transferase			
Glucose	Inorganic phosphorus			
Lactate dehydrogenase	Lipase			
Potassium	Sodium			
Total protein	Uric acid			
Hematology				

Hematology

Hematocrit
Platelets
White blood cell count and differential [1]

Hemoglobin Red blood cell count

- White blood cell count and differential [1]
 - 1. Manual microscopic review is performed only if white blood cell count and/or differential values are out of reference range.

Coagulation

International normalized ratio

Urinalysis

Bilirubin	Blood
Glucose	Ketones
Leukocyte esterase	Microscopy [1]
Nitrite	рН
Protein	Specific gravity
Urabilinagan	

Urobilinogen

1. Microscopy is performed only as needed based on positive dipstick test results.

Other tests

Urine pregnancy test (females of childbearing potential only)

6.6.3. Vital Signs

Vital signs will include temperature, blood pressure, heart rate, respiratory rate, oxygen saturation, and weight and will be collected at Screening, Baseline (pre-dose), daily on Study Days 2 through 4, and twice weekly thereafter during Study Drug Treatment, at EOST, EOT, and 2 and 4 weeks after EOT, or Early Termination. Height will be collected (from the patient's medical record) at Baseline.

6.6.4. APACHE II Score

The APACHE II score will be determined at Baseline (pre-dose).

6.6.5. Electrocardiograms

A 12-lead ECG will be obtained at Baseline (pre-dose), EOST, EOT, and 4 weeks after EOT, or Early Termination.

6.6.6. Physical Examinations

A complete physical examination will be conducted at Baseline (pre-dose). Complete physical examination will include an assessment of general appearance, skin, eyes, heart, chest, abdomen, the body site that corresponds to the entry site of candidemia (e.g., central venous catheter entry site), if applicable, and a neurological examination. Components of the neurological examination include cranial nerve, sensory and motor examination, reflex and gait testing, and coordination assessment.

A focused, symptom-based physical examination to include a neurological examination will be performed once weekly during study treatment, EOST, EOT, and 2 and 4 weeks after EOT, or Early Termination.

6.6.7. Pharmacokinetics

Plasma samples for PK (APX001 [prodrug] and APX001A [active moiety]) will be collected at Baseline (pre-dose), twice weekly during Study Drug Treatment, EOST, EOT, and 2 weeks after EOT, or Early Termination.

Optionally, if body fluids are sampled as part of routine patient management (e.g., bronchoalveolar lavage, lumbar puncture, paracentesis, vitreal fluid collection, abscess drainage), within approximately 2 hours of blood sampling for PK, these samples may be stored for future analysis of APX001 and APX001A levels.

6.6.8. Dilated Fundoscopic Examination

A dilated fundoscopic examination will be performed at Screening for all patients and at EOST, EOT, and 4 weeks after EOT, or Early Termination for those patients who had positive fundoscopic findings at Screening, or as clinically indicated.

6.6.9. Imaging Tests

Imaging should be performed to assess the site(s) and extent of candidemia infection as clinically indicated.

6.6.10. Other Cultures and Histopathology

Other cultures and histopathology should be performed to assess the site(s) and extent of candidemia infection as clinically indicated.

6.6.11. Intravascular Catheter/Device Management Log

The management of intravascular catheters, intravascular devices, and, if applicable, any drains will be recorded, including any associated microbiology results.

7. STATISTICAL METHODOLOGY

7.1. General Considerations

7.1.1. Summary Statistics

Summary statistics will be presented in total. For continuous variables, the number of observations (n), mean, standard deviation, median, minimum, and maximum will be provided. For categorical variables, the frequency and percentage in each category will be displayed.

For summary statistics, the mean and median will be displayed to one decimal place greater than the original value and the measure of variability (e.g. standard deviation) will be displayed to two decimal places greater than the original value.

7.1.2. Handling of Dropouts and Missing Data

Subjects who dropped out or had missing outcome data will be included in the denominator for efficacy analyses. A clinical failure occurring at an earlier time point will be carried forward to the subsequent visits.

In cases of missing or incomplete dates (e.g. Adverse event [AE] and concomitant medications), the missing component(s) will be assumed as the most conservative value possible. For example, AEs with missing start dates, but with stop dates either overlapping into the treatment period or missing, will be counted as treatment-emergent, taking the worst-case approach. When partial dates are present in the data, both a partial start date and/or a partial stop date will be evaluated to determine whether it can be conclusively established that the AE started prior to the start of study drug or ended prior to the start of study drug. If the above cannot be conclusively established based on the partial and/or present dates, then the AE will be considered as treatment-emergent. Actual data values as they appear in the original eCRF will be presented in the data listings.

Missing values for other variables will not be imputed and only observed values will be used in data analyses and summaries.

7.1.3. Baseline Definition

For microbiological data, baseline pathogen(s) are *Candida spp*. isolated from the last positive blood sample collected within 96 hours prior to the first dose of study drug.

For all efficacy and safety endpoints, baseline is defined as the last measurement or assessment prior to the first dose of study drug.

